## 6.7. Analysis of Secondary Endpoints

All secondary endpoints will be analyzed under the analysis population.

For URR and spKt/V for the first study use of both dialyzers, descriptive statistics will be presented, and 95% confidence intervals will be calculated if appropriate. These measurements observed/calculated for other timepoints (every 3-4 weeks) will be also presented with descriptive statistics.

For serum albumin and  $\beta_2$ -microglobulin, the relative percent change  $\{((\text{pre-HD} - \text{post-HD})/\text{pre-HD}) \times 100\}$  will be calculated. Descriptive statistics will be presented for the pre-HD and post-HD laboratory values and the relative percent change. Percent changes will also be calculated using corrected  $\beta_2$ -microglobulin concentrations based on the equation published by Bergström and Wehle. The 95% confidence interval will be derived if appropriate.

Adverse events will be coded for system organ class (SOC) and preferred term using Medical Dictionary for Regulatory Activities (MedDRA), Version 20.0. Adverse events and device-related events per treatment will be calculated. The 95% confidence intervals will be derived if appropriate.

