#### **4.2. Secondary Endpoint(s)**

The secondary endpoints include collecting the following data on the dialyzer with Endexo and the Optiflux dialyzer:

- The number of any adverse events and device-related adverse events.
- Urea Reduction Ratio (URR) and spKt/V (calculated from pre- and post-dialysis BUN) for the first study use of the dialyzers
- Pre- and post-HD serum albumin and  $\beta_2$ -microglobulin for the first use of dialyzers, visit 1 for Optiflux and visit 13 for dialyzer with Endexo.

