### **5. STATISTICAL METHODS**

#### **5.1. General Methodology**

There are multiple observations of one measurement for each subject in each period. All analyses will be performed at the subject level i.e., take average of multiple observations first of the measurement for each subject then analyze/summarize on subject averages.

Descriptive statistics (n, mean, standard deviation, median, minimum, and maximum) will be presented for continuous endpoints. Frequency and percent will be presented for categorical endpoints. Any missing values of an endpoint will not be imputed. All data entered collected will be listed.

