# 6. STATISTICAL ANALYSES

## 6.1. Disposition of Subjects

Frequencies will be for overall, by center, and for the treatment period.

The subject disposition table will include:

- The number of subjects who signed the informed consent.
- The number of subjects with screen failure.
- The number of subjects who were eligible.
- The number of subjects who were enrolled.
- The number of subjects who were discontinued in Optiflux, or in Endexo periods.
- The numbers of safety and analysis populations.
- The number of subjects and percent by category of major reasons for early discontinuation.

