## 6.3. Analysis Populations

- **Safety Population (spop):** The spop (safety population) will include subjects who sign the ICF, are eligible, are enrolled in the study, and have at least one HD treatment with the dialyzer with Endexo.
- **Analysis population (apop):** The apop (analysis population) will include subjects who are in the spop, and have a minimum of 36 HD treatments with the dialyzer with Endexo.

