## **6.9. Analysis of Safety**

All safety measurements will be analyzed under safety population

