### **6.9.1 Adverse Events**

See Section 6.7.

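### SAP 6.7 and 6.9 name different populations for adverse events, and no sentence says which one governs

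*SAP*

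**What the plan says.** SAP 4.2 lists as a secondary endpoint, for both dialyzers, "The number of any adverse events and device-related adverse events". SAP 6.7 opens with "All secondary endpoints will be analyzed under the analysis population" and then gives the only specification of the AE analysis: MedDRA coding, events per treatment, and 95% confidence intervals where appropriate. It makes no exception for AEs.

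SAP 6.9 opens with "All safety measurements will be analyzed under safety population". Its AE subsection, 6.9.1, consists of "See Section 6.7" and names no population.

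SAP 6.3 defines the analysis population (apop) as "subjects who are in the spop, and have a minimum of 36 HD treatments with the dialyzer with Endexo". The safety population (spop) needs only one Endexo treatment. The Statistical Methods entry of the protocol synopsis defines the same two populations and plans AE rates per treatment, but assigns neither population to them.

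**The concern.** Both opening sentences are unqualified, both cover AEs, and they point to different sets of subjects. A programmer who follows 6.9.1 arrives at a section whose first sentence names apop, and could cite the SAP for either choice. In an open-label study that choice should not be left until data have been seen.

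Summarising AEs with the Endexo dialyzer is the only secondary objective (SAP 1.2). If 6.7 governs, the AE rate is conditional on reaching 36 Endexo treatments, and an AE can be the reason a subject does not reach them. A subject who stopped Endexo after a device-related event would then be absent from the device-related rate and its confidence interval. The Optiflux-period rate would also be limited to subjects who later completed 36 Endexo treatments.

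**Working it through.** The plan states no figure to reproduce here. The check is a comparison of the texts, followed by arithmetic on what could differ.

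**1. Three readings of 6.7 and 6.9**
- 6.7 governs: AE rates in apop only. Subjects below 36 Endexo treatments enter no AE rate.
- 6.9 governs and 6.7 supplies only coding and method: AE rates in spop. Every subject with an Endexo treatment counts.
- Both apply: one AE table in apop (as a secondary endpoint) and one in spop (as safety). Every subject with an Endexo treatment enters at least one rate.

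No sentence selects among these.

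**2. Who separates the two populations**

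SAP 2.1 plans 38 Endexo treatments (visits 13 to 50) and allows up to four misses among visits 14 to 50.
- Two misses: 38 − 2 = 36, inside apop.
- Three misses: 38 − 3 = 35, outside.
- Four misses: 38 − 4 = 34, outside.

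So a subject who keeps to the missed-visit rule can still fall outside apop if the misses are not made up. Anyone who stops before 36 treatments is also outside.

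**3. How large the gap could be**

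The protocol synopsis plans 15 to 24 enrolled to obtain at least 12 with 36 treatments. If exactly 12 reach apop and every enrolled subject starts Endexo:
- 15 − 12 = 3, and 3/15 = 20%
- 24 − 12 = 12, and 12/24 = 50%

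This is an upper figure provided the target of 12 is met.

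**4. Effect on a device-related rate (assumed inputs)**

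Assume 12 apop subjects with 36 treatments each (12 × 36 = 432) and no device-related AE, plus one stopper with one such AE in m Endexo treatments, m from 1 to 35. The apop rate is 0. The spop rate depends on how events per treatment is computed:
- Pooled, 1/(432 + m): 1/467 = 2.1 per 1000 treatments at m = 35; 1/433 = 2.3 per 1000 at m = 1.
- Averaged by subject, (1/m)/13: (1/35)/13 = 2.2 per 1000 at m = 35; 1/13 = 76.9 per 1000 at m = 1.

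SAP 5.1 supports averaging ("All analyses will be performed at the subject level i.e., take average of multiple observations first of the measurement for each subject"), while the wording of 6.7 could also mean pooling.

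**5. Direction for all AEs (assumed inputs)**

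Let the 12 apop subjects have rate r and each of k stoppers have rate c × r, averaged by subject. Then apop = r and spop = r(12 + ck)/(12 + k), so apop/spop = (12 + k)/(12 + ck).

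| c | k = 1 | k = 3 |
|---|---|---|
| 2 | 13/14: apop 7.1% lower | 15/18: apop 16.7% lower |
| 1 | no difference | no difference |
| 0 | 13/12: apop 8.3% higher | 15/12: apop 25% higher |

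The sign depends on c, which the documents do not give.

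**The case against.** The strongest reply is that 6.9 is as unqualified as 6.7, that 6.9.1 is a subsection of it, and that a cross-reference for method need not import a population. The two sentences can also both be obeyed by producing two tables. On two of the three readings no subject with an Endexo treatment is missing from every AE rate. This stands, and it limits the point to an ambiguity with one harmful reading.

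The protocol's silence is also weak evidence. The supplied text is a synopsis that assigns no population to any endpoint.

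The size is soft as well. The 50% figure needs maximum enrolment with exactly half reaching apop. The 76.9 per 1000 figure arises because one event in one treatment gives that subject a rate of 1 under subject-level averaging; pooling gives 2.3 for the same data. Both criticisms are fair, so the figures serve only as illustrations under stated assumptions.

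A reader might go further and infer that the plan hides the events of subjects harmed by the device. The documents do not support that. SAP 5.1 states "All data entered collected will be listed", and the disposition table in SAP 6.1 includes "The number of subjects and percent by category of major reasons for early discontinuation". The events would be visible. What they might miss, if 6.7 governs, is the rate and its interval.

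**Conclusion.** The conflict is in the text and should be resolved before the tables are programmed. If 6.7 governs, AE rates exclude subjects with fewer than 36 Endexo treatments, including any who stopped because of an AE and any with three or four permitted misses not made up. If 6.9 governs, or both apply, those subjects are counted.

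The excluded share could be as high as 3 of 15 to 12 of 24 under the assumptions above. With about 12 subjects, a single device-related event in a stopper can decide whether the reported rate is zero or not.

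It is tempting to conclude that the AE rate is biased downward. That would follow only if 6.7 governs and the excluded subjects have more AEs per treatment than the rest. With equal rates there is no bias, and with fewer AEs the bias runs upward. The documents give neither an AE rate nor a dropout rate, so direction and size are unknown. The analysis is descriptive and no decision rule depends on it. This is a clarification worth making, not a fatal flaw.

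**What to change.** - **SAP 6.7:** limit the apop sentence to URR, spKt/V, albumin and beta-2-microglobulin.
- **SAP 6.9.1:** state that counts and per-treatment rates of AEs and device-related AEs, by period and for both dialyzers, use spop, and that any apop table is supportive only. Both periods need naming because 4.2 covers both dialyzers.
- **Optiflux-period stoppers:** spop requires an Endexo treatment, so enrolled subjects who stop during the Optiflux period are in neither population, although the protocol captures AEs from consent. Summarise their AEs separately.

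The cost is a few sentences in the SAP and slightly more table work, with no new data. The reported AE rate may look less favourable. If spop was already intended, the edit only records that intention.

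### Read literally, the averaging rule in SAP 5.1 lets a one-treatment subject weigh as much as a completer in the adverse event rate per treatment

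*SAP*

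**What the plan says.** SAP 5.1 sets a general rule: "All analyses will be performed at the subject level i.e., take average of multiple observations first of the measurement for each subject", after which the subject averages are summarised. It makes no exception for event rates.

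SAP 6.7 covers adverse events in two sentences: "Adverse events and device-related events per treatment will be calculated" and "The 95% confidence intervals will be derived if appropriate". It does not say how events and treatments are combined across subjects, or which interval is meant. The Statistical Methods row of the protocol synopsis is no more specific.

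Two populations are named for the same calculation. SAP 6.7 opens with "All secondary endpoints will be analyzed under the analysis population", and adverse events are among the secondary endpoints. SAP 6.9 says "All safety measurements will be analyzed under safety population", and the whole of 6.9.1 is "See Section 6.7". Under SAP 6.3, safety-population subjects "are enrolled in the study, and have at least one HD treatment with the dialyzer with Endexo", while analysis-population subjects must also "have a minimum of 36 HD treatments with the dialyzer with Endexo". Full Endexo exposure is 38 treatments (SAP 2.1).

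**The concern.** If the 5.1 rule is followed, each subject's events are divided by that subject's treatments and the resulting rates are averaged with equal weight. In the safety population, a subject with 1 event in a single Endexo treatment contributes a rate of 1.0 and counts as much as someone observed for 38 treatments.

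Short exposures are foreseeable. The protocol enrols 15-24 subjects to obtain at least 12 with 36 treatments, so if exactly 12 get there, 3 to 12 do not.

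Summarising adverse events is the trial's only secondary objective, and the rate per treatment is its main number. The distortion would also fall mostly on one side of any comparison between periods. A safety-population subject has already been through the Optiflux Period, where at most two treatments may be missed under SAP 2.1, so exposure there is nearly equal. SAP 2.2 allows the Optiflux measurements to serve as the control.

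A second question is what is reported for device-related events if none occurs, because an interval built on subject averages would then have no width.

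**Working it through.** The plan gives no adverse event rate, precision target or power figure, so there is nothing to reproduce. All event rates below are assumptions.

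**Inputs from the documents:** Endexo exposure of 1 to 38 treatments in the safety population and 36 to 38 in the analysis population; at least 12 completers.

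**Assumed:** 12 completers with 37 treatments each (12 × 37 = 444) and *r* events per treatment; *k* leavers, each with *a* events in *T* treatments.

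**Formulas**
- Mean of subject rates = (12*r* + *k* × *a*/*T*) / (12 + *k*)
- Pooled rate = (444*r* + *k* × *a*) / (444 + *k* × *T*)

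**Leavers who had an event**

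| *r* | Leavers | Mean of rates | Pooled | Ratio |
|---|---|---|---|---|
| 0.05 | 1, with 1 event in 1 treatment | 1.6/13 = 0.123 | 23.2/445 = 0.052 | 2.4 |
| 0.05 | 2, with 1 event in 1 treatment | 2.6/14 = 0.186 | 24.2/446 = 0.054 | 3.4 |
| 0.05 | 1, with 1 event in 3 treatments | 0.933/13 = 0.072 | 23.2/447 = 0.052 | 1.4 |
| 0.05 | 2, with 1 event in 3 treatments | 1.267/14 = 0.090 | 24.2/450 = 0.054 | 1.7 |
| 0.02 | 3, with 1 event in 1 treatment | 3.24/15 = 0.216 | 11.88/447 = 0.027 | 8.1 |
| 0.10 | 1, with 1 event in 3 treatments | 1.533/13 = 0.118 | 45.4/447 = 0.102 | 1.16 |

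The last two rows are the extremes over backgrounds of 0.02 to 0.10, one to three leavers, and exits after 1 or 3 treatments. The effect shrinks with more completers: 23 completers with 2 events in 38 treatments each, plus one leaver with 1 event in 1 treatment, give 0.092 against 47/875 = 0.054, a ratio of 1.7. It also shrinks with later exit: 12 such completers and three leavers with 1 event in 10 treatments give 1.12.

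**Event-free leavers.** Take 12 completers with 2 events in 38 treatments each and three leavers with 0 events in 1 treatment. The mean of rates is (12 × 2/38)/15 = 0.042 and the pooled rate is 24/459 = 0.052, a ratio of 0.81.

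**Exit unrelated to events.** Take 12 subjects with 38 treatments, three with 1, and Poisson counts at 0.05 per treatment. Both estimators are unbiased.
- Variance of the mean of rates = (12 × 0.05/38 + 3 × 0.05/1)/15² = 0.000737, SD 0.027
- Variance of the pooled rate = 0.05/459 = 0.000109, SD 0.010
- Variance ratio about 6.8

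**Analysis population.** The most unequal case with 12 subjects puts every event in one subject with 36 treatments while the other 11 have 38. The ratio is then (36 + 11 × 38)/(12 × 36) = 454/432 = 1.05. The mirror case gives (38 + 11 × 36)/(12 × 38) = 434/456 = 0.95.

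**No device-related event.** At an assumed 0.001 per treatment, the chance of none in 444 treatments is exp(−0.444) = 0.64. A t or Wald interval on 12 zero averages is 0 to 0. The exact Poisson upper limit is −ln(0.025)/444 = 0.0083 per treatment.

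**The case against.** The strongest reply is that the SAP never says the adverse event rate is a mean of subject rates. Events per treatment can naturally be read as a total over a total. SAP 4.2 lists the endpoint as a count. The rule in 5.1 is introduced by repeated observations of one measurement, which suits laboratory values better than event counts. Where the SAP wants a per-subject quantity, as for full clotting in 6.8, it says so. This stands: the pooled reading is available. It does not settle the matter, because 5.1 covers all analyses and two programmers could follow the same text to results several-fold apart.

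A reader might also infer that the reported rate will be several times too high. The documents do not support that. It takes very early exit, an event in the subject who leaves, and a low background rate. Event-free leavers push the rate down, and unrelated exit costs precision only. Section 6.7 also names the analysis population, where the weighting hardly matters.

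Nor do the documents support inferring that the plan commits to a 0-to-0 interval. No interval method is named, and the SAP may omit an interval judged not appropriate. What remains is that nothing is specified for zero events.

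Finally, the study is descriptive, has no decision rule on adverse events, and lists all data, so an early leaver's events would be visible. That limits the harm but does not make the summary rate sound.

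**Conclusion.** The point holds as a conditional weakness. Read literally, 5.1 gives a poor estimator of the adverse event rate in the safety population, and 6.7 does nothing to override it. Under the assumed rates, the result is 2.4 to 3.4 times the pooled rate with one or two one-treatment leavers who each had an event. It is about 0.8 times with three event-free ones, and carries about 6.8 times the variance when exit is unrelated to events. In the analysis population the effect is at most about 5%, so the conflict between 6.7 and 6.9 over the population decides whether the weighting matters. The zero-width interval arises only if a t or Wald method is applied to subject averages. The size of each effect rests on assumed event rates and exit patterns; that the rule covers event rates and that exposure is unequal come from the documents. This should be corrected, but it does not threaten the primary endpoint.

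**What to change.** - In SAP 5.1, exempt event rates from the subject-averaging rule.
- In SAP 6.7 and 6.9.1, define the rate for all adverse events and for device-related events as total events divided by total treatments, by period, in the safety population. Naming the population there also resolves the conflict between 6.7 and 6.9.
- Give a 95% interval from a bootstrap that resamples subjects, so that clustering within subject is respected. With 12 to 24 subjects it is approximate and should be described as such.
- When no event occurs, report the exact Poisson upper limit, noting that it takes no account of clustering.
- Report the number of subjects with at least one event beside each rate.
- The mean of subject rates may stay as a supportive line.

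The cost is SAP wording and a few lines of code, with no new data. Rows with no events will show an upper limit above zero (0.0083 per treatment at 444 treatments) where a t or Wald interval would show 0 to 0.

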## 6.8. Analysis of Exploratory Assessments

All exploratory assessments will be analyzed under analysis population.

For the measurements of complement activation, the relative percent change  $\{((30 \text{ minutes after the recorded start of HD} - \text{pre-HD})/\text{pre-dialysis}) \times 100\}$  will be calculated. Descriptive statistics

will be presented for the “pre-dialysis” and “30 minutes after the recorded start of HD” laboratory values and the relative percent change. The 95% confidence intervals will be calculated if appropriate.

For thrombus formation:

- the number of subjects and percentages, and the number of dialysis treatments in each period for each grade category will be presented, and,
- the proportion of treatments with full dialyzer clotting will be calculated for each subject in each period. Descriptive statistics of the proportions will be presented. A 95% confidence interval of the proportions will be calculated if appropriate.

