1.0 PROTOCOL SYNOPSIS

Title	An Open-Label Clinical Study to Assess the Performance of the Dialyzer with Endexo™ in End-Stage Renal Disease Subjects
Protocol Number	Endexo-001
Study Type	Open-label single-arm clinical trial
Investigational Products	
Dialyzer with Endexo™ ("F5"), Fresenius Medical Care North AmericaOptiflux® dialyzer (F160NR), Fresenius Medical Care North America (cleared under 510(k) number K152367)
Proposed Indication	The dialyzers with Endexo are a series of single-use, high-flux dialyzers intended for treatment of patients with acute or chronic renal failure when conservative therapy is judged to be inadequate. The dialyzers with Endexo must be used in conjunction with dialysis machines equipped with ultrafiltration control and are to be used only as directed by a physician.
Study Objectives	
The primary objective of the study is to collect data on the performance of the dialyzer with Endexo when used to perform hemodialysis (HD) in End-Stage Renal Disease (ESRD) subjects.
 
The secondary objective is to collect and summarize adverse events with the dialyzer with Endexo when used to perform HD in ESRD subjects.

Study Design	This is a prospective, sequential, multi-center, open-label study with subjects on thrice-weekly (in-center) HD. After a Screening Period, there will be 12 HD treatments on the Optiflux dialyzer (Optiflux Period), followed by 38 HD treatments on the dialyzer with Endexo (Endexo Period), and then a Follow-up Visit.

Study Population	The study population will consist of ESRD subjects who are a minimum of 22 years of age, have been prescribed in-center thrice weekly HD continuously for at least 180 days prior to the date of signed informed consent, and have been prescribed the Optiflux F160NR dialyzer continuously for at least 30 days prior to the date of signed informed consent.
Total Number of Subjects	15-24 enrolled subjects, to achieve at least 12 subjects with a minimum of 36 HD treatments per subject on the dialyzer with Endexo
Total Number of Sites	3-4 (United States)

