## 2. STUDY DESIGN

### 2.1. General Description

This is a prospective, sequential, multi-center, open-label study with subjects on thrice-weekly (in-center) hemodialysis treatment.

Each subject will participate in a screening period, Optiflux period, Endexo period, and a follow-up visit.

- Screening Period

Screening, which will be up to 4 weeks in duration, begins with signing of the informed consent form (ICF). After the Screening Period is completed (with eligibility verified), the subject is enrolled and can proceed to the Optiflux Period.

- Optiflux period

The Optiflux Period is 12 HD treatments (visits 1 to 12) on the Optiflux dialyzer (4 weeks in duration). A maximum of two missed treatments are permitted within visits 2 to 11. The visit 12 cannot be missed during the Optiflux period.

- Endexo period

The Endexo period is 38 HD treatments on the dialyzer with Endexo (approximately 13 weeks in duration). The visit 13 cannot be missed. A maximum of four missed treatments are permitted within Visits 14-50.

- Follow-up visit

An in-center Follow-up visit is to be conducted within 1 week of the last scheduled study HD treatment.

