#### **4.3. Additional Assessments**

The following data will be collected on the dialyzer with Endexo and the Optiflux dialyzer.

- Complement activation (C3a, C5a, SC5b-9) during the first study use of the dialyzer, collected pre-HD and at 30 minutes ( $\pm 10$  minutes) after the recorded start of HD,
- Thrombus scoring, performed at the end of dialyzer use for every dialyzer used in the study,
- Urea Reduction Ratio (URR) and spKt/V every 3-4 weeks,
- Total volume (mL) of saline flush for each treatment, frequency and rate per HD treatment when using to treat clotting during HD.

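### SAP 6.8 summarises dialyzer clotting only in subjects with at least 36 Endexo treatments, so Endexo clotting can be understated if anyone stops early because of clotting

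*SAP*

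**What the plan says.** SAP 4.3 and the protocol synopsis (Additional Assessments) both provide for "Thrombus scoring, performed at the end of dialyzer use for every dialyzer used in the study". Scores therefore exist for every Endexo treatment given, including those of subjects who leave early.

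SAP 6.8 sets the population for the summaries: "All exploratory assessments will be analyzed under analysis population". Two thrombus outputs fall under it. One is a table of grades by period. For the other, "the proportion of treatments with full dialyzer clotting will be calculated for each subject in each period", followed by descriptive statistics and a confidence interval if appropriate.

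SAP 6.3 defines two populations. Safety-population subjects "have at least one HD treatment with the dialyzer with Endexo". Analysis-population subjects must also "have a minimum of 36 HD treatments with the dialyzer with Endexo".

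On exposure, SAP 2.1 says "The Endexo period is 38 HD treatments on the dialyzer with Endexo" and also "A maximum of four missed treatments are permitted within Visits 14-50".

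The protocol synopsis (Statistical Methods) describes the same thrombus outputs and names no population for them.

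**The concern.** Membership of the analysis population is settled by what happens after Endexo starts, and clotting is one of the things that could shorten exposure. A first-use reading at visit 13 comes from a single treatment. Clotting is summarised over up to 38 treatments, and repeated clotting could itself be why a subject stops. Selection into the summary could then depend on the outcome being summarised, and the subjects removed would be those with the most clotting.

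The primary objective is dialyzer performance, and clotting is a performance measure taken at every treatment. From the planned tables a reader could not tell whether a low clotting proportion describes the device or only the subjects who stayed on it for about 13 weeks.

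**Working it through.** **1. Does another section bring the early stoppers back?**
- SAP 6.9 uses the safety population, but its subsections cover adverse events, laboratory tests, vital signs, physical findings and medications. Thrombus is not among them.
- The adverse-event entry (6.9.1) refers back to 6.7, which names the analysis population.
- SAP 5.1 lists all data, and SAP 6.1 counts major reasons for early discontinuation. Neither gives a clotting rate.
- The protocol's missing-at-random statement and SAP 5.4 (no imputation) concern missing values. These scores are observed and are excluded by the population rule.

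**2. How tight is the cut-off?** 38 − 36 = 2, so a subject with three or more Endexo treatments not given falls outside. The four permitted misses leave 38 − 4 = 34, also below 36, unless missed treatments are made up, which the documents do not say. A subject within the attendance rule can thus be excluded.

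**3. How much can one subject matter?** Assume 15 subjects: 14 complete 38 treatments with 1% full clotting, and one stops with 2 full clots in 10 treatments.
- Analysis population: 1.0%.
- Safety population, mean of subject proportions: (14 × 0.01 + 0.20)/15 = 2.3%.
- Safety population, clots over treatments: (14 × 38 × 0.01 + 2)/(14 × 38 + 10) = 7.32/542 = 1.35%.

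**4. A range under clotting-driven stopping.** The plan has no figure to reproduce here, so every input except 38 and 36 is an assumption. Each subject has a full-clot probability per treatment from a beta distribution with mean m and first shape parameter a (0.5 = strong variation between subjects, 50 = almost none). Treatment ends at the second or third full clot, or at 38. The ratio below is full clots over all Endexo treatments given, divided by the mean proportion in subjects reaching 36 (simulation, 400,000 subjects per cell).

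| Mean rate m | a = 0.5, 2nd / 3rd clot | a = 2, 2nd / 3rd | a = 50, 2nd / 3rd |
|---|---|---|---|
| 0.5% | 1.4 / 1.1 | 1.2 / 1.0 | 1.2 / 1.0 |
| 1% | 1.7 / 1.2 | 1.4 / 1.1 | 1.3 / 1.0 |
| 2% | 2.3 / 1.5 | 1.8 / 1.2 | 1.6 / 1.1 |
| 4% | 3.1 / 2.0 | 2.4 / 1.6 | 2.1 / 1.4 |

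At m = 2%, a = 0.5 and second clot, 17% of subjects fall outside the analysis population. Its rate is 0.7%, against 1.6% over all treatments given.

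**5. Control.** With 20% of subjects leaving at times unrelated to clotting, the analysis population returns 1.0% for a true 1% and 3.0% for a true 3%. There is no bias.

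**6. Does the safety population give the right answer?** In the 2% scenario of step 4, the safety-population mean of subject proportions is 3.1%, above the true 2.0%. Stopping occurs on a clot, so a short, clot-heavy record counts as much as a full one. Clots over all treatments gives 1.6%, somewhat low but much closer than 0.7%.

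**The case against.** The case for leaving the plan alone is that thrombus scoring is an additional, exploratory assessment in a small descriptive study. Nothing supplied says that anyone stops, or must stop, for clotting. Only the protocol synopsis is available, so any withdrawal criteria cannot be checked. The scores are listed and stopping reasons are tabulated, so no data are lost. All of this stands, and it limits the weight of the point. It does not supply a clotting summary that includes early stoppers.

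Three stronger readings are tempting, and the documents do not support them.

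- **That Endexo clotting is understated as a matter of fact.** This needs at least one subject to stop before treatment 36 because of clotting. Without that the bias is nil, and a subject who stops at or after treatment 36 stays in the summary.
- **That 20% to 50% of subjects are exposed to the problem.** The plan is for "15-24 enrolled subjects, to achieve at least 12 subjects with a minimum of 36 HD treatments per subject", which gives (15 − 12)/15 = 20% and (24 − 12)/24 = 50%. Those are margins among enrolled subjects, and 24 is a ceiling on enrolment. They include anyone who leaves during the 12 Optiflux treatments, and so has no Endexo score and is outside the safety population too, as well as anyone who falls short through missed visits alone.
- **That an Optiflux–Endexo comparison is biased towards Endexo.** The same subjects are dropped from both periods, so the effect partly cancels if they are clot-prone on both dialyzers. It has not been computed, and SAP 5.2 only says such comparisons may be made.

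**Conclusion.** The point holds in conditional form. By a stated rule, the clotting summary omits the scores of any subject who stops Endexo before treatment 36. If clotting is the reason, the Endexo figure is biased low. Under the assumptions tabulated, the rate over all Endexo treatments is about 1.0 to 3.1 times the analysis-population rate. The top of that range needs a 4% mean rate, strong variation between subjects and stopping at the second clot. The low end applies when full clots are rare and subjects are alike. The documents give none of these inputs, so the range is illustrative and not a forecast. The effect on a between-period comparison is uncertain. The change is worth making because it is cheap and answers a question that the planned tables cannot, although the assessment is exploratory.

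**What to change.** In SAP 6.8:
- Run the thrombus grade table and the full-clotting summary in the safety population, by period, over every scored dialyzer.
- Lead with full-clot treatments divided by all treatments, with a 95% interval that allows for clustering by subject. State this as an exception to the subject-average rule in SAP 5.1.
- Show the per-subject proportions beside it, with a note that their mean is biased upward when subjects stop on a clot.
- Keep the analysis-population version as supportive.

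Separately, the four permitted missed Endexo visits in SAP 2.1 and the 36-treatment minimum in SAP 6.3 must be reconciled.

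The cost is SAP wording and one extra run of existing tables, with no new data. The downside for the sponsor is a clotting figure that may be slightly less favourable. If nobody stops because of clotting, the two versions should differ only by chance, and the report can show that.
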